7.5. Safety Measurements

Physical Examination, Height and Weight

A complete physical examination to include documentation of height (at Screening) and weight will be performed by a physician or staff member who is qualified to perform such examinations (eg, physician's assistant, nurse practitioner). Any abnormal or clinically significant findings from the physical examination must be recorded in the appropriate eCRF. Findings at screening and prior to dosing on Day 1 will be recorded as medical history.

At study visits in which a complete physical examination is required, the investigator should perform a thorough examination of all body systems (exception: genitourinary and reproductive should be symptom-directed). At study visits in which a limited physical examination is required, the investigator should inquire about signs/symptoms, general appearance, eyes (pupillary reaction, ophthalmoscopy, eye movements), oral mucosa, heart and pulses, lungs, abdomen (liver/spleen), kidneys, and neurological (symptom-directed and may include mental state, speech, gait/posture, arm swinging, facial movements, tongue, muscle wasting [power and tone], coordination, reflexes, and sensation.)

Vital Signs

Vital sign measurements will be collected after the subject has been sitting for 5 minutes. Vital sign assessments will include measurements of sitting blood pressure (mm Hg), heart rate (beats per minute), respiration rate (breaths per minute), and temperature (Celsius). Predose vital signs should be collected within 4 hours prior to dosing, and postdose vital signs should be taken within \pm 15 minutes of the scheduled time point.

Blood pressure measurements are to be performed using appropriate technique (per guidelines of the American Heart Association). Specifically, subjects should be seated quietly for at least 5 minutes in a chair with their backs supported, their legs uncrossed, and their arms bared on a hard surface, with the arm slightly abducted and bent, with palm up and the midpoint of upper arm at heart level. The correct cuff and bladder size should be utilized and recorded. Two or more readings separated by 1–2 minutes should be averaged. If the first 2 readings differ by more than 5 mm Hg, 1 or 2 additional readings should be obtained and averaged.

Electrocardiogram

Electrocardiograms will be performed with the subject in a supine position having rested in this position for at least 5 minutes before each reading. Triplicates should be obtained, with an interval of 1-2 minutes between ECGs.

During the study, all ECGs will be digitally analyzed by a validated central ECG vendor. Additional details on collection of ECGs will be provided in a separate manual.

The QT interval will be corrected using Fridericia's formula, adapted from Fridericia, 1920 12:

$$QT_F = \frac{QT}{RR^{1/3}}$$

All subjects must demonstrate an average screening QTcF value of \leq 450 msec by central digital analysis in order to be enrolled in the study. During the study, immediate clinical management of subjects will be based on results of machine-read ECGs at the sites. However, the central digital analysis will prevail as it becomes available. In addition, the central digital analysis will be used for any AE and SAE documentation.

An increase in QTcF interval (by central digital analysis) to a value > 60 msec above baseline or to the level of ≥ 480 msec requires further monitoring and, after collection of a PK blood sample and discussion with the Medical Monitor on appropriate management, the subject may be removed from the trial (see guidelines in Section 6.7.1.2).

Abnormalities in the ECG that lead to a change in subject management (eg, requirement for additional medication or monitoring) or result in clinical signs and symptoms are considered clinically significant for the purposes of this study and will be recorded on the AE eCRF. If ECG abnormalities meet criteria defining them as serious, they must be reported as an SAE (see Section 8.2.3).

Echocardiogram

Echocardiograms for determination of ejection fraction and evaluation of pericardial effusion and cardiac valve function will be collected at the time points specified in Table 2.

Ocular Monitoring

Ocular monitoring will be performed at the time points specified in Table 2. Ocular monitoring will include an assessment of best corrected distance visual acuity, fundoscopic exam with non-dilated pupils, slit lamp photography of the iris, non-mydriatic photography of retina within the arcade, and optical coherence tomography of the optic nerve head and macula.

Clinical Laboratory Evaluations

A central laboratory will perform clinical laboratory evaluations.

The Investigator should assess out-of-range clinical laboratory values for clinical significance, indicating if the value(s) is/are not clinically significant or clinically significant.

Abnormalities in clinical laboratory tests that lead to a change in subject management (eg, dose delay, requirement for additional medication or monitoring) are considered clinically significant for the purposes of this study, and will be recorded on the AE eCRF page.

Abnormal clinical laboratory values, which are unexpected or not explained by the subject's clinical condition may be, at the discretion of the Investigator or Sponsor, repeated until confirmed, explained, or resolved as soon as possible. If laboratory values constitute part of an event that meets criteria defining it as serious, the event (and associated laboratory values) must be reported as an SAE (see Section 8.2.3).

At the investigator's discretion, any subset of the laboratory panels in Table 6 may be duplicated in local laboratories for an immediate medical assessment. However, inclusion and

exclusion criteria as well as the final statistical analysis will be based on results from the central laboratory.

Table 6: Clinical Laboratory Tests

	Serum Chemistry		
• albumin	• BUN	 phosphorous 	
 amylase 	• calcium	• potassium	
 alkaline phosphatase 	• chloride	random glucose	
• ALT	• creatinine	• sodium	
• AST	CPK (plus CPK isoenzymes	total & direct bilirubin	
• bicarbonate	if CPK is elevated)	• total protein	
	 lactate dehydrogenase 	• magnesium	
	Hematology		
RBC count	hemoglobin	• MCV	
WBC with differential	hematocrit	• MCH	
(including neutrophils,	platelet count	• MCHC	
basophils, eosinophils, lymphocytes, monocytes)			
Tymphocytes, monocytes)			
	Coagulation	Г	
• PT	• PTT	• INR	
	Urinalysis		
• appearance	• leukocytes	occult blood (microscopic	
• color	• protein	examination of sediment	
• pH	• glucose	will be performed only if the results of the urinalysis	
 specific gravity 	bilirubin	dipstick evaluation are	
• ketones	 urobilinogen 	positive)	
Other			
Creatinine clearance ^a	• cystatin C	• TSH	
• Pregnancy test ^b	• fasting triglycerides ^c	Hepatitis and HIV ^f	
•	• lipase ^d	• HbA1c ^f	
	• amylase isoenzymes ^e		
	• CPK isoenzymes ^f		

Abbreviations: ALT, alanine aminotransferase; AST, aspartate aminotransferase; BUN, blood urea nitrogen; CPK, creatine phosphokinase; HbA1c, glycated hemoglobin; HIV, human immunodeficiency virus; INR, international normalized ratio; MCH, mean cell hemoglobin; MCHC, mean cell hemoglobin concentration; MCV, mean cell volume; PT, prothrombin time; PTT, partial thromboplastin time; RBC, red blood cell; TSH, thyroid stimulating hormone; ULN, upper limit of normal; WBC, white blood cell

a. To be calculated using serum creatinine (Modification of Diet in Renal Disease-4 variable formula).

- b. Pregnancy tests will be done using urine samples. A positive test result (confirmed by serum testing) will require immediate discontinuation from the study.
- c. To be collected in the event that serum amylase increases to $> 1.5 \times ULN$
- d. To be collected at Screening and in the event of that serum amylase increases to $> 1.5 \times ULN$
- e. To be collected in the event that CPK increases to $> 2.0 \times ULN$.
- f. To be collected only at Screening.

Concomitant Medications

Prior and concomitant medications will be recorded throughout the study (from Screening through 28 days following the last dose of study drug). Refer to Section 5 for details on concomitant medications that should be avoided or taken with caution during the study.

Adverse Events

At each study visit, subjects will be questioned in a general way to ascertain if AEs have occurred since the previous visit (eg, "Have you had any health problems since your last visit?"). Adverse events collection is detailed in Section 8.

7.6. Efficacy Measurements

Magnetic Resonance Imaging

Magnetic resonance imaging measurements will be used to explore the efficacy of tesevatinib. Kidney volume will be determined by MRI at the time points specified in Table 2.

The volume of each kidney should be measured in T1-weighted images with use of a stereologic method and calculated from the set of contiguous images by summing the products of the area measurements and slice thickness. Height-adjusted total kidney volume is calculated using total kidney volume obtained from MRI divided by height in meters.

8. ADVERSE AND SERIOUS ADVERSE EVENTS ASSESSMENT

8.1. Definition of Adverse Events, Period of Observation, Recording of Adverse Events

An *Adverse Event* (AE) is any untoward medical occurrence in a clinical investigation subject administered a pharmaceutical product and that does not necessarily have a causal relationship with this treatment. An AE can therefore be any unfavorable and unintended sign (including an abnormal laboratory finding), symptom, or disease temporally associated with the use of a medicinal (investigational) product, whether or not related to the medicinal (investigational) product.

All AEs should be captured on the AE eCRF.

Findings at screening and prior to dosing on Day 1 will be recorded as medical history. Where possible, a diagnosis, rather than a list of symptoms, should be recorded. If a diagnosis has not been made, then each symptom should be listed individually. In addition to untoward AEs, unexpected benefits outside the investigational product indication should also be captured on the AE eCRF.

All AEs must be followed to closure (the subject's health has returned to his/her baseline status or all variables have returned to normal), an outcome is reached, stabilization (the Investigator does not expect any further improvement or worsening of the event), or the event is otherwise explained regardless of whether the subject is still participating in the study. When appropriate, medical tests and examinations are performed so that resolution of event(s) can be documented.

Severity Categorization

The severity of AEs must be recorded during the course of the event including the start and stop dates for each change in severity. An event that changes in severity should be captured as a new event. Worsening of pre-treatment events, after initiation of investigational product, must be recorded as new AEs (for example, if a subject experiences mild intermittent dyspepsia prior to dosing of investigational product, but the dyspepsia becomes severe and more frequent after first dose of investigational product has been administered, a new AE of severe dyspepsia [with the appropriate date of onset] is recorded on the appropriate eCRF).

The medical assessment of severity is determined by the 5-point Clinical Symptom and Adverse Event Grading Scale provided in Table 7.

Table 7: 5-point Clinical Symptom and Adverse Event Grading Scale

Clinical Adverse Event Grading Scale			
Severity	Grade	Definition	

Mild	1	Awareness of symptom, but easily tolerated. Usually transient requiring no special treatment; does not interfere with usual status or activities
Moderate	2	May be ameliorated by simple therapeutic measures; may interfere with usual activities
Severe	3	Incapacitating; unable to perform usual activities
Life-threatening	4	Requires immediate intervention; need for emergency treatment
Death	5	Resulting in the subsequent death of the subject

Relationship Categorization

A Physician/Investigator must make the assessment of relationship to investigational product for each AE. The Investigator should decide whether, in his or her medical judgment, there is a reasonable possibility that the event may have been caused by the investigational product. If there is no valid reason for suggesting a relationship, then the AE should be classified as 'not related'. Otherwise, if there is any valid reason, even if undetermined or untested, for suspecting a possible cause-and-effect relationship between the investigational product and the occurrence of the AE, then the AE should be considered 'related'. The causality assessment must be documented in the source document.

The additional guidance in Table 8 may be helpful.

 Table 8:
 Relationship Assessment for Adverse Events

Term	Relationship	Definition
Definitely Related	Yes	The event is felt to be related to the administration of the study drug. The relationship of an AE to the study drug can be considered related if:
		 It follows a reasonable temporal sequence from administration of the drug or drug levels have been established in body fluids or tissues;
		• It could not be reasonably explained by the known characteristics of the subject's clinical state, environmental or toxic factors or other modes of therapy administered to the subject; and
		It disappears or decreases* upon cessation of drug or reduction on dose and appears upon rechallenge;
		• It follows a known response pattern to the suspected drug.
		*There are exceptions when an AE does not disappear upon discontinuation of the drug, yet drug relatedness clearly exists.
		The first 3 criteria must be met for the event to be considered definitely related.
	Yes	The event is felt with a high degree of certainty to be related to the administration of study drug. The relationship can be considered probably related if:
		• It follows a reasonable temporal sequence from the administration of study drug;
Probably Related		• It could not be reasonably explained by the known characteristics of the subject's clinical state, environment or toxic factors or other modes of therapy administered to the subject; and
		 It disappears or decreases upon cessation of drug or reduction of dose;*
		• It follows a known response pattern to the suspected drug.
		*There are exceptions when an AE does not disappear upon discontinuation of the drug, yet drug relatedness clearly exists.
		The first 3 criteria must be met for the event to be considered probably related.

Term	Relationship	Definition
Possibly Related	Yes	The event is felt to be unlikely due to the administration of study drug but the possibility cannot be ruled out with certainty. The relationship to study drug can be considered possibly related if:
		It follows a reasonable temporal sequence from the administration of study drug; and
		 It could readily have been the result of the subject's clinical state, environmental or toxic factors, or other modes of therapy administered to the subjects;
		• It follows a known response pattern to the suspected drug. The first 2 criteria must be met for the event to be considered possibly related.
Unlikely Related	No	The event is felt to be unlikely due to the administration of study drug after careful medical consideration. The relationship to study drug can be considered unlikely related if:
		• It does not follow a reasonable temporal sequence from administration of the drug; and
		• It could readily have been a result of the subject's clinical state, environmental or toxic factors, or other modes of therapy administered to the subjects;
		 It does not follow a known response pattern to the suspected drug;
		 It does not reappear or worsen when the drug is re- administered.
		The first 2 criteria must be met for the event to be considered unlikely related.
Not Related	No	The event is felt to be due to extraneous causes (disease, environment, etc.) that are not related to the administration of study drug.

Outcome Categorization

The outcome of AEs must be recorded during the course of the study on the CRF. Outcomes are as follows:

- Resolved
- Resolved with Sequelae
- Ongoing
- Death
- Unknown

Symptoms of the Disease Under Study

Symptoms of the disease under study should not be classed as AEs as long as they are within the normal day-to-day fluctuation or expected progression of the disease. However, significant worsening of the symptoms should be recorded as an AE.

Clinical Laboratory Evaluations

A change in the value of a clinical laboratory investigation can represent an AE if the change is clinically relevant or if, during treatment with the investigational product, a shift of a parameter is observed from a normal value to an abnormal value, or a further worsening of an already abnormal value. When evaluating such changes, the extent of deviation from the reference range, the duration until return to the reference range, either while continuing treatment or after the end of treatment with the investigational product, and the range of variation of the respective parameter within its reference range, must be taken into consideration.

If, at the end of the treatment phase, there are abnormal clinical laboratory values which were not present at baseline, further clinical or laboratory investigations should be performed until the values return to within the reference range or until a plausible explanation (eg, concomitant disease) is found for the abnormal clinical laboratory values.

The Investigator should decide, based on the above criteria and the clinical condition of a subject, whether a change in a clinical laboratory parameter is clinically significant and therefore represents an AE.

Pregnancy

All pregnancies are to be reported from the time informed consent is signed until the defined follow-up period stated in Table 2.

Any report of pregnancy for any female subject or the partner of a male subject must be reported within 1 business day to the Pharmacovigilance vendor (see Table 1). The female subject must be withdrawn from the study.

Every effort should be made to gather information regarding the pregnancy outcome and condition of the infant. It is the responsibility of the Investigator to obtain this information within 30 calendar days after the initial notification and approximately 30 calendar days post-partum.

Pregnancy complications such as spontaneous abortion/miscarriage or congenital abnormality are considered SAEs and must be reported within 24 hours using the Serious Adverse Event Form. Note: An elective abortion is not considered an SAE.

In addition to the above, if the Investigator determines that the pregnancy meets serious criteria, it must be reported as an SAE using the Serious Adverse Event Form as well as the Pregnancy Report Form. The test date of the first positive serum/urine pregnancy test or ultrasound result will determine the pregnancy onset date.

Overdose and Medication Error

Any medication error that results in an AE, even if it does not meet the definition of serious, requires reporting within 24 hours to the Medical Monitor. An overdose of study drug without any associated signs or symptoms, unless the subject is hospitalized for observation, will not constitute an AE but will be recorded as a protocol deviation.

Cases of subjects missing doses of product are not considered reportable as medication errors.

Medication errors should be collected/reported for all products under investigation. The administration and/or use of the unassigned treatment is always reportable as a medication error. The administration and/or use of an expired product should be considered as a reportable medication error.

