- 13. Subject is taking any medication known to inhibit the cytochrome P450 (CYP)3A4 isozyme or any drugs that are CYP3A4 inducers, or any drugs associated with torsade de pointes or known to prolong the QTcF interval, including anti-arrhythmic medications within 2 weeks prior to screening. A stable regimen (≥ 4 weeks) of antidepressants of the selective serotonin reuptake inhibitor (SSRI) class is allowed (common SSRIs include escitalopram oxalate, citalopram, fluvoxamine, paroxetine, sertraline, and fluoxetine).
- 14. Uncontrolled intercurrent illness that would limit compliance with study requirements including, but not limited to ongoing or active infections or psychiatric illness.
- 15. Subject is pregnant, plans to become pregnant, or nursing.

16. Known to be positive for the human immunodeficiency virus or hepatitis B or C, as indicated by a positive test at screening.

- 17. Known to be immunocompromised.
- 18. Documented presence of renal vascular disease resulting in uncontrolled hypertension.
- 19. Has previously received an epithelial growth factor receptor (EGFR) inhibitor (including, but not limited to, erlotinib, gefitinib, osimertinib, afatinib, cetuximab, panitumumab, or an investigational agent).
- 20. Allergy or hypersensitivity to components of either tesevatinib, matched placebo, or their formulations.
- 21. Aphakic due to previous cataract surgery or congenital abnormality.

Note: The sponsor has the option to exclude a subject from enrollment, if, based upon the subject's medical history or screening results, it is felt that a subject's safety may be at risk and/or if the safety data may confound the study results.

Maximum duration of subject involvement in the study:

The planned duration of the screening period is no more than 28 days prior to dosing (42 days for MRI and ocular assessments). The planned duration of treatment period is approximately 730 days (or 24 months). The follow-up period will be 30 days from the last dose of study drug.

Endpoints and statistical analysis:

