Informed consent	>					
Medical and PKD history (include genotype, if available)	*					
Physical examination ^d (including weight)	~	~	~	~	~	~
Vital signs ^e	~	~	~	~	~	~
Supine 12-lead ECG ^f	~	~	~	~	~	~
Clinical laboratory tests ^g	~	~	~	~	~	~
Ocular evaluation ^h	>				•	>
Echocardiogram ⁱ	>			~	~	~
Pregnancy test ^j	>	~		~	~	~
MRI ^k	•				(every 6 months beginning at Month 12)	•
Randomization		~				
Study drug/placebo dispensed		~	~	*	~	>
Record adverse events	>	~	~	~	~	~
Record concomitant medication	>	~	~	*	•	>
Drug compliance/collection ¹		~	~	~	~	~

Abbreviations: ECG, electrocardiogram; MRI, magnetic resonance imaging; PKD, polycystic kidney disease; QTc(F), QT interval corrected for heart rate using Fridericia's formula; TSH, thyroid stimulating hormone

- a. Screening evaluations may be combined with Day 1 pre-treatment laboratory evaluations if both are done within 4 days before first dose of study drug. Screening MRI and ocular assessments may be performed up to 6 weeks prior to Day 1.
- b Follow-up treatment period visits to be performed monthly (every 28 ± 1 day). For those subjects continuing on study beyond 12 months, visits will occur every 2 months ± 3 days between Months 12 and 24.
- c. The End-of-study visit is to be performed 30 days (± 3 days) after last dose of study drug.
- d. A complete physical examination is to be done at the Screening and End-of-study visits. Height will only be measured at Screening. Symptom-driven physical examinations will be performed on Days 1, 14, 28, every 28 days from Months 2 to 12, and every 2 months from Months 12 to 24. See Section 7.5.1 for a description of the body systems and evaluations to be performed at each visit (eg, cardiac tamponade, ocular toxicity and xerostomia assessments).
- e. Vital sign measurements will include sitting blood pressure, heart rate, respiratory rate, and oral or tympanic temperature. On Day 1, measurements should be performed predose and 1 and 4 hours postdose. See Section 7.5.2 for details on vital signs measurement.

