- f. Supine 12-Lead ECGs will be performed at Screening, predose, 1, 4, and 8 hours postdose on Days 1 and 14; predose on Days 28 and Months 2 to 12, at each visit on Months 12 to 24; and at the End-of-study visit. Supine ECGs should be repeated 3 times consecutively within 30 minutes (with an interval of at least 1-2 minutes between ECGs). If QTc(F) is prolonged to > 60 msec above baseline at any evaluation or to the level of ≥ 480 msec based on local ECG read, refer to Section 6.7.1.2 for a description of the procedures to be followed.
- g. Clinical laboratory tests will include hematology, serum chemistry, coagulation, TSH, and urinalysis (see Section 7.5.6 for a complete list of assessments). Thyroid stimulating hormone levels will be evaluated at Screening and then every 2 months. Serology testing will be done at Screening only.
- h. Ocular evaluations are to be performed at Screening and at Months 3, 6, 9, 12, 18, and 24, and at the End-of-study visit (if applicable). The following assessments will be performed: evaluation of best corrected visual acuity, fundoscopic exam with non-dilated pupils, slit lamp photography of the iris, non-mydriatic photography of retina within the arcade, and optical coherence tomography of the optic nerve head and macula. Note: if a subject has had ocular evaluations within 3 months of the End-of-study visit, there is no need to repeat ocular evaluations at the End-of-study visit.
- i. Echocardiograms are to be obtained at Screening, on Day 28, at Months 3, 6, 12, 18, and 24, and at the End-of-study visit (if applicable). Echocardiograms should include measurement of ejection fraction and assessment for pericardial effusion and valvular abnormalities. Note: If a subject has had an echocardiogram within 3 months of the End-of-study visit, there is no need to obtain an echocardiogram at the End-of-study visit. If pericardial effusion is diagnosed via echocardiogram, the subject should be rechecked within 1–3 months to monitor for progression.
- j. Pregnancy testing in women of childbearing potential will be performed using urine samples. Subjects must have a negative urine pregnancy test documented within the 24-hour period prior to the first dose of study drug. Pregnancy tests are to be performed at Screening, predose on Day 1, Day 28, Month 3, every 3 months through Month 12, at every visit between Months 12 and 24, and at the End-of-study visit only. Positive urine samples will be confirmed via serum testing.

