- Sexually active women of childbearing potential enrolled in the study must agree to use 2 forms of accepted methods of contraception during the course of the study and for 6 months after their last dose of study drug. Effective birth control includes (a) intrauterine device **plus** 1 barrier method; (b) on stable doses of hormonal contraception for at least 3 months (eg, oral, injectable, implant, and transdermal) **plus** 1 barrier method; or (c) 2 barrier methods. Effective barrier methods are male or female condoms, diaphragms, and spermicides (creams or gels that contain a chemical to kill sperm); or (d) a vasectomized partner.
- 8. For male subjects who are sexually active and are partners of premenopausal women: agreement to use two forms of contraception as in criterion 7 above during the treatment period and for at least 6 months after the last dose of study drug, unless the male subject had a vasectomy.
- 9. Capable of understanding and complying with the protocol and has signed the informed consent form.

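### Pregnancy reporting stops about 30 days after the last dose while required contraception runs for 6 months, leaving about 5 post-dose months with no clear duty to report

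*Protocol*

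**What the plan says.** **Reporting period.** Protocol Section 8.1.6 (Pregnancy) states: "All pregnancies are to be reported from the time informed consent is signed until the defined follow-up period stated in Table 2". Table 2, footnote c, fixes that follow-up: "The End-of-study visit is to be performed 30 days (± 3 days) after last dose of study drug". The synopsis agrees: "The follow-up period will be 30 days from the last dose of study drug".

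**Contraception period.** Section 4.1, criterion 7, binds sexually active women of childbearing potential "during the course of the study and for 6 months after their last dose of study drug". Criterion 8 binds sexually active men with premenopausal partners "during the treatment period and for at least 6 months after the last dose of study drug, unless the male subject had a vasectomy".

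**Testing.** Table 2, footnote j, schedules urine tests for women of childbearing potential, the last of them "at every visit between Months 12 and 24, and at the End-of-study visit only". No test is scheduled for the partners of male subjects.

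**Other rules that bear on the point:**
- Section 8.1.6 also requires a pregnancy in a female subject or a male subject's partner to be passed on within 1 business day. That sentence gives no end date of its own.
- The same section classes miscarriage and congenital abnormality as SAEs, says that an elective abortion is not one, and asks for outcome information to about 30 days post-partum.
- It dates the onset of a pregnancy by the first positive test or ultrasound.
- Section 8.3 keeps an open-ended duty after the study, but only for SAEs that the investigator discovers and considers related.

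**The concern.** The protocol asks subjects to avoid conception for 6 months after the last dose, yet closes its pregnancy reporting at about 1 month. A subject or partner who becomes pregnant in the third month after the last dose is inside the period in which the protocol asks for contraception and outside the period in which it asks to hear of a pregnancy. No later contact is scheduled, and the last test falls at the End-of-study visit.

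The protocol takes pregnancy seriously elsewhere: two contraceptive methods, repeated testing, withdrawal on pregnancy and reporting within 1 business day. What is at stake is the completeness of pregnancy and outcome data for an investigational drug. If late cases come in only when an outcome is both adverse and judged related, there is no count of late pregnancies against which to set those outcomes.

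**Working it through.** The plan states no figure on this point, so this is interval arithmetic on its own periods.

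**Inputs**
- Post-dose contraception: 6 months (criteria 7 and 8), taken as 365.25/12 × 6 = 182.6, or about 183 days.
- End of reporting: day 30 after the last dose, or day 27 to 33 with the visit window (Table 2, footnote c).
- Planned treatment: 24 months, about 730 days (synopsis).

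**Step 1: post-dose days with no clear reporting duty** = contraception days − reporting days
- Day 30: 183 − 30 = 153 days, about 5.0 months
- Day 33: 183 − 33 = 150 days
- Day 27: 183 − 27 = 156 days

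**Step 2: share of the post-dose segment**
- 150/183 = 82%; 153/183 = 84%; 156/183 = 85%
- Taking 6 months as 180 or 184 days widens the range only to 147–157 days (180 − 33 and 184 − 27), still 82–85%.

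**Step 3: share of the whole contraception period for a 24-month completer**
- Whole period: 730 + 183 = 913 days, about 30 months
- 153/913 = 17%
- The post-dose gap is the same for a subject who stops earlier, but its share of the whole period is larger.

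**Step 4: conceptions before day 30**

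The gap is not confined to conceptions after day 30. Onset is the date of the first positive test or ultrasound, so a pregnancy conceived shortly before the End-of-study visit, and not yet detectable there, has an onset date after reporting closes. For partners of male subjects there is no scheduled test at all. A conception late in treatment or during follow-up may become known only after the subject's last visit. The documents give no basis for a count of such cases.

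**Step 5: what the remaining rules catch after day 30**

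| Late event | Required to be reported? |
|---|---|
| Miscarriage or congenital abnormality, learned of and judged related | Yes, Section 8.3 |
| The same, judged unrelated | Not under Section 8.3 |
| Uncomplicated pregnancy | Not under Section 8.3; unclear under Section 8.1.6 |
| Elective abortion | Not an SAE; unclear under Section 8.1.6 |

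The entries marked unclear turn on the 1-business-day sentence. It follows directly after the sentence that sets the period, and is most naturally read as saying how fast and to whom reports within that period go.

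**The case against.** **Washout.** Section 1.2.1.3 gives a mean terminal half-life of 50 to 92 hours. Thirty days is 720 hours, which is 720/92 = 7.8 to 720/50 = 14.4 half-lives. Even at the slow end less than 0.5% of the drug would remain (0.5^7.8 ≈ 0.0045). A long contraception margin and a shorter collection period can coexist. This stands as far as it goes: a reader might infer that the protocol says a fetus is exposed for 6 months, and it does not. But the protocol gives no reason for the two periods to differ, and the washout argument does not reach conceptions late in treatment or soon after the last dose that surface after reporting closes.

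**Other routes.** A reader might also infer that no late pregnancy could be reported. That goes too far. The 1-business-day sentence is undated, miscarriage and congenital abnormality are SAEs, and Section 8.3 is open-ended for related ones. The threshold for related is low: Section 8.1.2 accepts any valid reason for suspicion, and Table 8 counts a possible relationship as related. Voluntary reports also remain possible. This narrows the loss. It does not remove it, because Section 8.3 depends on the investigator learning of the event and does not cover uncomplicated or unrelated cases.

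**Missing pages.** The consent pages were not available for review, and an instruction to notify the site of later pregnancies may be there. Its absence therefore cannot be asserted. It would not in any case change the period stated in Section 8.1.6.

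**Conclusion.** The mismatch is real and should be reconciled. About 5 of the 6 post-dose contraception months (150 to 156 days, 82–85% of that segment) carry no clear duty to report a pregnancy. For a 24-month completer this is about 17% of the whole contraception period.

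These are shares of days. It would be tempting to conclude that most pregnancies in the contraception period would be missed. The documents do not support that: on-treatment pregnancies are covered, and no pregnancy rate is given.

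The point concerns sexually active women of childbearing potential and sexually active, non-vasectomized men with premenopausal partners, not every subject. Their number is not stated.

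The conclusion rests on two readings: that the follow-up period in Table 2 ends at the End-of-study visit, and that the undated 1-business-day sentence falls within the reporting period. If the wording of Section 8.1.6 were taken to mean that reporting ends when follow-up begins, the gap would be the full 6 months; the conclusion does not rely on that.

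The consequence is incomplete safety collection, mainly of uncomplicated or unrelated late pregnancies and their outcomes. The primary and other efficacy analyses are unaffected.

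**What to change.** Reconcile Section 8.1.6 with criteria 7 and 8:

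1. In Section 8.1.6, let the reporting period for pregnancies in female subjects and in partners of male subjects run to the end of the protocol's own post-dose contraception period.
2. State there, and next to the follow-up duration in the synopsis and Table 2, that this is an exception to the 30-day follow-up.
3. At the End-of-study visit, instruct subjects to notify the site of any pregnancy, their own or a partner's, until that date. Carry the same instruction into the consent form if it is not already there.
4. Keep the existing outcome follow-up in Section 8.1.6 for these pregnancies, and make clear that the 1-business-day rule applies to them.

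The cost is protocol wording, possibly consent wording, and one instruction at an existing visit. No visit, test or contraception rule changes. The downside is that sites will handle occasional reports after a subject's last visit and follow those pregnancies to about 30 days post-partum, which can fall well after the subject has left the study.
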